16.3 Safety Profile

- 16.31 Adverse events will be graded and attribution assigned using CTC CAE version 4.0. For each type of toxicity reported, the proportion of patients experiencing a severe level of that toxicity will be determined.

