1.6 Preclinical and clinical Trial Data

- 1.61 The clinical trial data for pembrolizumab for the treatment of patients with metastatic melanoma has been previously published in detail. In summary, pembrolizumab induces durable remissions in a sizable minority of patients with metastatic melanoma (20-40%) with an acceptable safety profile of less than 10% grade 3 or 4 adverse events.
- 1.62 Imiquimod is a toll-like receptor 7 (TLR7) agonist approved for the treatment of basal cell carcinoma and genital warts. Imiquimod was tested in a randomized phase three study of patients with superficial basal cell carcinoma. (2) In this study, imiquimod induced histologic clearance in 80% of patients compared with 3% in the control arm with less than 10% of patients experiencing a severe (grade 3 or 4) adverse event. In the setting of genital warts, imiquimod 5% cleared 72-

84% of warts with a complete remission rate of 40-70% with few recurrences (5-19%). (3)

- 1.63 There are several reports demonstrating the clinical activity of imiquimod in treating cutaneous melanoma. In 2000, imiquimod 5% induced a complete remission in one patient with lentigo maligna melanoma. [1] In 2002, topical imiquimod 5% induced a complete remission in a patient with invasive melanoma however the patient did eventually develop lymph node metastases. [2] Also in 2002, Bong et al reported 3 patients with cutaneous metastases treated topical imiquimod with excellent responses in 2/3 of patients with the third patient achieving a response when combining imiquimod with intra-lesional interleukin-2. [3] Taken together, topical imiquimod is effective at controlling some patients with cutaneous melanoma but not at preventing distant metastases.

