1.7 Rationale

- 1.71 Approximately 20% of patients with metastatic melanoma are burdened with surgically unresectable cutaneous disease. The standard of care for these patients is systemic therapy as there are no FDA approved agents to apply directly to the skin. While systemic therapy can sometimes generate response in patients' cutaneous lesions, a topical therapy that could assist the systemic therapy would be highly desirable.
- 1.72 Multiple topical agents have been utilized to treat cutaneous melanoma with variable success. Imiquimod is a topical immune modulator thought to activate the toll-like receptor (TLR) pathway and help the body produce interferon locally to increase the activity of the immune system. Imiquimod is approved for the use of variety of skin disorders including basal cell carcinoma, actinic keratosis, and genital warts. Several studies have explored the efficacy of imiquimod to treat cutaneous melanoma and have demonstrated activity. There are no studies combining the use of imiquimod with pembrolizumab.
- 1.73 A case series reports successfully treated two patients with the combination of ipilimumab and imiquimod[7]. In both patients, cutaneous tumors substantially grew while on ipilimumab only to regress after the addition of imiquimod. Both patients tolerated the combination well and both patients have a durable remission of 9-12 months.

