- 1.9c11 Clinical Efficacy Endpoint- The expected single agent response rate of pembrolizumab is ~40% in the front line setting and ~25% when given after progression on ipilimumab. Given the small number of patients to be enrolled onto this trial, we will construct a 90% confidence interval for the proportion of patients who have a CR or PR on two consecutive evaluations at least 6 weeks among all the patients enrolled on this trial.
- 1.9c12 Clinical Safety Endpoint - Given the non-overlapping toxicities of pembrolizumab and imiquimod, we expect serious toxicities to occur at a rate similar to each drug individually. For example, pembrolizumab induces serious adverse events in ~10% of patient and imiquimod induces serious adverse events in 1-3% of patients. Therefore we expect ~10-13% of patient to experience a serious adverse event.

1.9d Biomarker Research

One of the largest unmet needs in improving the therapeutic potential of pembrolizumab is identifying reliable predictive biomarkers. In this study, the biomarker research will be exploratory in nature and will include assessing total tumor RNA through RNA seq and PDL1 expression through the use of immunohistochemistry. Attempts will then be made to associate molecular markers with clinical outcomes.

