2.0 Goals

2.1 Primary

To gain preliminary data of the anti-tumor activity and safety profile of the combination of imiquimod and pembrolizumab in patients with unresectable cutaneous melanoma.

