8.0 Dosage Modification Based on Adverse Events

8.1 Dose-Modification Guidelines for Drug Related Adverse Events for Pembrolizumab

CTCAE System/Organ/Class (SOC)	ADVERSE EVENT	Hold Treatment for Grade	Timing for Restarting Treatment	Discontinue Subject
Gastrointestinal disorders	Diarrhea/Colitis	2-3	AE resolves to Grade 0-1	Toxicity does not resolve within 12 weeks of last dose or inability to reduce corticosteroid to 10mg or less of prednisone or equivalent per day within 12 weeks.
		4	Permanently discontinue	Permanently discontinue
Investigations	AST, ALT, or Blood bilirubin	2	AE resolves to Grade 0-1	AE does not resolve within 12 weeks of last dose
		3-4	Permanently discontinue (see exception below) ^a	Permanently discontinue
Metabolism and nutrition disorders	Glucose intolerance (Type 1 diabetes mellitus [if new onset] or Hyperglycemia)	Type 1 diabetes mellitus or 3-4	Hold pembrolizumab for new onset Type 1 diabetes mellitus or Grade 3-4 hyperglycemia associated with evidence of beta cell failure.	Resume pembrolizumab when patients are clinically and metabolically stable.
Endocrine disorders	Hypophysitis	2-3	AE resolves to Grade 0-1	AE does not resolve within 12 weeks of last dose or inability to reduce corticosteroid to 10mg or less of prednisone or equivalent per day within 12 weeks
		4	Permanently discontinue	Permanently discontinue
Endocrine disorders	Hyperthyroidism	3	AE resolves to Grade 0-1	AE does not resolve within 12 weeks of last dose or inability to reduce corticosteroid to 10 mg or less of prednisone or equivalent per day within 12 weeks.
		4	Permanently discontinue	Permanently discontinue

CTCAE System/Organ/Class (SOC)	ADVERSE EVENT	Hold Treatment for Grade	Timing for Restarting Treatment	Discontinue Subject
Endocrine disorders	Hypothyroidism	2-4	Therapy with pembrolizumab can be continued while treatment for the thyroid disorder is instituted	Therapy with pembrolizumab can be continued while treatment for the thyroid disorder is instituted.
General disorders and administration site conditions	Infusion reaction	3-4	Permanently discontinue	Permanently discontinue
Respiratory, thoracic and mediastinal disorders	Pneumonitis	2	AE resolves to Grade 0-1	AE does not resolve within 12 weeks of last dose or inability to reduce corticosteroid to 10mg or less of prednisone or equivalent per day within 12 weeks.
		3-4	Permanently discontinue	Permanently discontinue

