Renal and urinary disorder	Acute kidney injury or Chronic kidney disease (e.g. Renal failure or Nephritis)	2	AE resolves to Grade 0-1	AE does not resolve within 12 weeks of last dose or inability to reduce corticosteroid to 10 mg or less of prednisone or equivalent per day within 12 weeks.
		3-4	Permanently discontinue	Permanently discontinue
	All Other Drug Related Adverse Events ²	2	AE resolves to Grade 0-1	AE does not resolve within 12 weeks of last dose or inability to reduce corticosteroid to 10 mg or less of prednisone or equivalent per day within 12 weeks
		3-4	Permanently discontinue	Permanently discontinue

* Located at [REDACTED]

NOTE: Permanently discontinue Treatment for any severe or Grade 3 drug-related AE that recurs or any life-threatening event.

^aFor patients with liver metastasis who begin treatment with Grade 2 AST or ALT, if AST or ALT increases by greater than or equal to 50% relative to baseline and lasts for at least 1 week then patients should be discontinued.

^bPatients with intolerable or persistent Grade 2 drug-related AE may hold study medication at physician discretion. Permanently discontinue study drug for persistent Grade 2 adverse reactions for which treatment with treatment with study drug has been held, that do not recover to Grade 0-1 within 12 weeks of the last dose.

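### Section 16.31 summarizes only severe toxicity; a maximum-grade table would cheaply add the Grade 2 events that can end pembrolizumab

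*Combined protocol and SAP*

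**What the plan says.** Section 2.1 states a single primary goal with two halves: "To gain preliminary data of the anti-tumor activity and safety profile of the combination of imiquimod and pembrolizumab". Section 16.31 provides for adverse events to be graded and attributed under CTCAE version 4.0, and then commits to one statistic. For each type of toxicity reported, "the proportion of patients experiencing a severe level of that toxicity will be determined".

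Section 16.3 does not define severe. Elsewhere the protocol ties the word to Grade 3 or higher. Section 1.62 describes an imiquimod trial with "less than 10% of patients experiencing a severe (grade 3 or 4) adverse event", and the note under the 8.1 table reads "Permanently discontinue Treatment for any severe or Grade 3 drug-related AE that recurs". Section 10.1 warns that severe and serious are different things.

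Section 8.1 makes some Grade 2 events treatment-limiting for pembrolizumab. The discontinuation condition for hypophysitis and pneumonitis is "AE does not resolve within 12 weeks of last dose or inability to reduce corticosteroid to 10mg or less of prednisone"; the steroid limit is a daily dose and carries the same 12-week deadline. Footnote b adds that patients with "intolerable or persistent Grade 2 drug-related AE may hold study medication at physician discretion", and that the drug is stopped for good if such an event has not recovered within 12 weeks.

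Section 10.621 requires related Grade 2 events to be submitted on the case report forms. Section 16.6 has the study statistician report adverse events to the DSMB every six months, and 16.61 sets a stopping rule on related Grade 4 events.

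**The concern.** The rationale says "There are no studies combining the use of imiquimod with pembrolizumab" (1.72), so this trial is meant to supply a first look at how the pair is tolerated. A safety profile normally tells the reader which events limited treatment as well as which were severe. Here the protocol's own dose rules treat several Grade 2 immune events as reasons to stop pembrolizumab, yet the only statistic it defines starts higher.

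Followed as written, the summary would give no sign of a patient taken off pembrolizumab for Grade 2 pneumonitis or colitis that failed to resolve. What is at stake is the completeness of a descriptive summary in 10 patients.

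**Working it through.** The plan gives no numerical figure for this safety summary, so there is none to reproduce. The check is a comparison of 8.1 with 16.31, followed by an attempt to size the gap.

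**Step 1. Which rows of 8.1 let a Grade 2 event end pembrolizumab?**

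| Row in 8.1 | Held at Grade 2? | Permanent if unresolved at 12 weeks? | Also permanent if steroid not down to 10 mg by 12 weeks? |
|---|---|---|---|
| Diarrhea/colitis | Yes | Yes | Yes |
| AST, ALT or bilirubin | Yes | Yes | No |
| Glucose intolerance | No (new type 1 diabetes, or Grade 3-4) | – | – |
| Hypophysitis | Yes | Yes | Yes |
| Hyperthyroidism | No (from Grade 3) | – | – |
| Hypothyroidism | No (treatment continues) | – | – |
| Infusion reaction | No (Grade 3-4) | – | – |
| Pneumonitis | Yes | Yes | Yes |
| Renal | Yes | Yes | Yes |
| All other related events | Yes, at physician discretion (taking footnote b to govern this row) | Yes | Yes |

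That is 5 of 9 named rows, plus the row for all other events. The steroid condition applies in 4 of those 5 and in the row for all other events. It matters at Grade 2 because section 9.6 guides toward systemic steroids at that grade for diarrhea lasting more than a week (9.613), hypophysitis (9.641) and pneumonitis (9.652).

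**Step 2. Does any defined output show these events?**

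- 16.31: no, if severe means Grade 3 or higher.
- 16.61: no; it counts related Grade 4 events.
- 16.6: possibly. The six-monthly report has no grade limit, but no table or statistic is specified, and it serves monitoring.
- 1.9c12: no. It states an expectation, "Therefore we expect ~10-13% of patient to experience a serious adverse event", and no analysis.

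**Step 3. Are the data there?** Yes. Any related Grade 2 event is captured, either as a term graded at each evaluation under 10.61 or through 10.621. The gap is in the summary and not in collection.

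**Step 4. What does one patient do to the summary?** Take 10 evaluable patients, one of whom stops pembrolizumab for unresolved Grade 2 pneumonitis, with no severe case. The 16.31 entry for pneumonitis is 0/10 = 0%. A maximum-grade table would show 1/10 = 10% at Grade 2, with one related discontinuation.

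**Step 5. How often would this happen?** With true rate p, the chance of at least one case in 10 patients is 1 − (1 − p)^10. The only rates available are the pembrolizumab rates in 15.17, and applying them to the combination is an assumption.

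- Hypophysitis and autoimmune nephritis are the only two with a Grade 2 rate, each below 1%. The chance is below 1 − 0.99^10 = 0.0956, about 9.6%, for each.
- Colitis, pneumonitis and renal failure are listed at 1% to 10% with no grade. For any grade the chance runs from 9.6% to 1 − 0.90^10 = 0.651, about 65%, for each. The Grade 2 part is no larger than this and is not given.
- Diarrhea and raised AST are listed above 10%, also with no grade.

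No rate is given for Grade 2 holds overall, and permanent discontinuation is a subset of those. These figures do not size the gap.

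**The case against.** The strongest reply is that the chosen statistic is the right one for this pilot. There is no safety hypothesis, the proportions are descriptive, and the background rates in 1.61 and 1.62 are themselves for Grade 3 or 4 events, so a severe proportion is what can be compared with them. Imiquimod is the added drug, and both hold triggers listed for it in 8.2, local skin reaction and flu-like symptoms, are at Grade 3 and so are captured. The omission therefore concerns only pembrolizumab, an approved drug with a listed toxicity profile, and 1.9c12 expects the two drugs' toxicities not to overlap. Nothing in 16.31 forbids a further table, and the DSMB reports may show lower grades along the way.

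Most of this stands, and it is why the priority is low. It does not remove the point. Being free to add a table is not a commitment to one, the DSMB report has no specified content by grade, and 2.1 promises a safety profile of the combination.

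A reader might infer three stronger things that the documents do not support:

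- That the severe proportions are wrong or misleading. They are correct for what they measure.
- That Grade 2 toxicity goes unrecorded. Section 10.621 collects it when related.
- That a missed case is likely. The range up to 65% is for events of any grade, and the Grade 2 share is unknown.

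**Conclusion.** The point holds as a modest improvement of low priority. Section 16.31 is accurate but incomplete as a summary of half the primary goal: it commits to showing none of the related Grade 2 events that 8.1 allows to end pembrolizumab. The size is 10 percentage points per affected patient, given 10 evaluable patients; the expected number of such patients cannot be derived from the documents.

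Two readings carry this conclusion. First, severe in 16.31 means about Grade 3 or higher, which is inferred from 1.62 and the note under 8.1 because 16.3 has no definition; if the sponsor meant something wider, the section needs to say so. Second, the DSMB reports are monitoring documents and not the trial's safety summary. The efficacy analysis is unaffected.

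**What to change.** In 16.31, state that severe means Grade 3 or higher, keep those proportions, and add:

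- a table of the maximum CTCAE v4.0 grade per patient for each toxicity type, once for all events and once for events at least possibly related;
- the number of patients who permanently discontinued pembrolizumab for a related event, by grade of that event.

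Footnote the table: Grade 1 events, and unrelated Grade 2 events, outside the 10.61 list are not required to be collected, so those cells may be incomplete.

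Leave out a count of temporary holds unless the reason for a hold is already recorded. The Data Submission Schedule and the forms are not in the documents, so this cannot be checked here. The discontinuation count likewise assumes that the reason for stopping is recorded; 13.3 lists unacceptable toxicity among the criteria for stopping.

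The cost is two or three sentences and one extra table for 10 patients, with no new visits, tests or data items.

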16.4 Progression-free and overall survival

- 16.41 Progression-free survival time is defined as the time from registration to documentation of first disease progression or death due to any cause. Survival time is defined as the time from registration to death due to any cause.
- 16.42 The duration of response and the distributions of OS times and PFS times will be estimated using the Kaplan-Meier method.

16.5 Biomarker changes during treatment

- 16.51 Biomarkers will be assessed prior to treatment and 6 and 12 weeks following the start of treatment. For each patient and each biomarker, a times-series plot of biomarker value will be constructed. These graphs will be visually examined for trends within and between the group of patients whose tumor responded to treatment and the group of patients whose tumor did not respond to treatment.
- 16.52 Plots of the percent change in biomarker level at 6 weeks versus response (yes vs. no) to visually assess whether the percent change in biomarker level at 6 weeks tends to be greater for one group versus the other. This will be repeated for the value of the biomarker at 6 weeks to gain insight into whether it is the amount of the change or where the biomarker lands after 6 weeks of treatment that separates the two groups.

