2.3 Correlative Research

To compare and contrast (in a hypothesis generating manner) the biomarker profiles of patients who have a confirmed CR or PR by RECIST criteria with patients who do not. Immunologic markers to be assessed include tumor-infiltrating lymphocytes (TIL), tumor expression of programmed death ligand one (PDL1), and toll-like receptor 7.

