11.4 Measurement of Effect

11.41 Target Lesions & Target Lymph Nodes

- Measurable lesions (as defined in Section 11.21) up to a maximum of 5 lesions, representative of all involved organs, should be identified as “Target Lesions” and recorded and measured at baseline. These lesions can be non-nodal or nodal (as defined in 11.21), where no more than 2 lesions are from the same organ and no more than 2 malignant nodal lesions are selected.

Note: If fewer than 5 target lesions and target lymph nodes are identified (as there often will be), there is no reason to perform additional studies beyond those specified in the protocol to discover new lesions.

- Target lesions and target lymph nodes should be selected on the basis of their size, be representative of all involved sites of disease, but in addition should be those that lend themselves to reproducible repeated measurements. It may be the case that, on occasion, the largest lesion (or malignant lymph node) does not lend itself to reproducible measurements in which circumstance the next largest lesion (or malignant lymph node) which can be measured reproducibly should be selected.
- Baseline Sum of Dimensions (BSD): A sum of the longest diameter for all target lesions plus the sum of the short axis of all the target lymph nodes will be calculated and reported as the baseline sum of dimensions (BSD). The BSD will be used as reference to further characterize any objective tumor response in the measurable dimension of the disease.
- Post-Baseline Sum of the Dimensions (PBSD): A sum of the longest diameter for all target lesions plus the sum of the short axis of all the target lymph nodes will be calculated and reported as the post-baseline sum of dimensions (PBSD). If the radiologist is able to provide an actual measure for the target lesion (or target lymph node), that should be recorded, even if it is below 0.5 cm. If the target lesion (or target lymph node) is believed to be present and is faintly seen but too small to measure, a default value of 0.5 cm should be assigned. If it is the opinion of the radiologist that the target lesion or target

lymph node has likely disappeared, the measurement should be recorded as 0 cm.

- The minimum sum of the dimensions (MSD) is the minimum of the BSD and the PBSD.

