16.0 Statistical Considerations and Methodology

16.1 This pilot study will enroll 10 patients to gain preliminary data on the anti-tumor activity and safety profile of the combination of imiquimod and pembrolizumab in patients with unresectable cutaneous melanoma.

If there are no tumor responses documented among these 10 patients, then upper bound of a one-sided 95% confidence interval for the tumor response rate would be 25.9%.

All patients meeting the eligibility criteria who have signed a consent form and have begun treatment will be evaluable for assessment of all of the clinical endpoints.

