17.4 Background and Methodology

17.41 Immunohistochemistry will be performed to assess expression of PDL1, PD1, CD3, CD8, and CD4. These markers will be assessed both at baseline, 6 weeks, and 12 weeks in both the lesion treated with imiquimod and untreated lesion (when available). We will analyze the possible association of baseline expression as well as change in expression with response to treatment.

17.42 RNA expression of a panel of immune related genes will be assessed using Nanostring immune panel of 500+ immune related genes. We will analyze the possible associations of baseline and change in baseline immune genes with response to treatment in the lesion treated with imiquimod and untreated lesions (when available).

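### The responder versus non-responder marker comparison uses outcome only as yes/no in 10 patients; a plot against percent change in tumour size, from data already collected, would show more at little cost

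*Combined protocol and SAP*

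**What the plan says.** The correlative goal in Section 2.3 is to compare "biomarker profiles of patients who have a confirmed CR or PR by RECIST criteria with patients who do not", and it is labelled hypothesis generating. Section 16.51 plots each marker over time per patient and looks by eye for trends within and between responders and non-responders. Section 16.52 adds "Plots of the percent change in biomarker level at 6 weeks versus response (yes vs. no" and repeats this for the 6-week marker value. Section 17.41 states: "We will analyze the possible association of baseline expression as well as change in expression with response to treatment". Section 17.42 says much the same for a panel of more than 500 immune genes. No marker analysis has a stated test, significance level, effect size or power.

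The tumour data are richer than yes/no. Measurable disease is an entry criterion (Section 3.15). Section 11.41 has the sum of dimensions calculated at baseline (BSD) and after baseline (PBSD), and says "The BSD will be used as reference to further characterize any objective tumor response in the measurable dimension of the disease". Partial response is a 30% decrease in that sum (Section 11.432).

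On numbers, Section 16.1 says "This pilot study will enroll 10 patients to gain preliminary data on the anti-tumor activity and safety profile" and considers the case of no responses. Section 1.9c11 says "The expected single agent response rate of pembrolizumab is ~40% in the front line setting and ~25% when given after progression on ipilimumab". No rate is given for the combination.

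**The concern.** Response yes/no is largely a cut of a continuous measure that the trial already collects. Once cut, a patient with 29% shrinkage is grouped with one who progressed. With so few patients the responder group will be very small, and in some trials empty or a single patient. Section 16.1 allows for that ("If there are no tumor responses documented among these 10 patients"), but Section 16.5 does not say what is then shown.

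Section 16.52 asks whether the size of the marker change or the level reached at 6 weeks separates the groups. With one or two responders that question can hardly be answered by eye, and chance separation is common. Serial biopsies are taken to answer it, so the display should use the outcome information at hand. The RECIST cut for the response-rate endpoint itself is not in question.

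**Working it through.** **Inputs from the documents.** n = 10 (16.1); response rate p = 0.25 to 0.40 (1.9c11, single agent); marker outcome yes/no (2.3, 16.52); BSD and PBSD recorded (11.41).

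**Inputs assumed.** Marker and tumour change bivariate normal with correlation 0.3 to 0.8; two-sided 5% level. The documents give neither.

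**Step 1: the plan's own figure.** The upper one-sided 95% bound with 0 of 10 responders is 1 − 0.05^(1/10) = 25.9%, as stated in Section 16.1.

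**Step 2: size of the responder group.** The expected number is 10 × 0.25 = 2.5 to 10 × 0.40 = 4.

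- P(0) = (1 − p)^10: 0.75^10 = 5.6%; 0.60^10 = 0.6%.
- P(0 or 1) = (1 − p)^10 + 10p(1 − p)^9: 24.4% at 25%; 4.6% at 40%.

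**Step 3: what one or two responders can show.** For a marker unrelated to outcome and without ties, the chance that k responders are perfectly separated from the rest, in either direction, is 2/C(10, k): 2/10 = 20% for k = 1, 2/45 = 4.4% for k = 2, 2/120 = 1.7% for k = 3, 2/210 = 1.0% for k = 4. Over 500 unrelated genes that is about 100, 22, 8 and 5 perfect separations by chance.

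**Step 4: information kept by the cut.** Under bivariate normality the fraction is φ(z_p)² / [p(1 − p)], where φ is the normal density at the cut.

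- p = 0.25: 0.3178² / 0.1875 = 0.54.
- p = 0.40: 0.3863² / 0.24 = 0.62.

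This is as if 10 patients were about 5 to 6.

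**Step 5: power as a yardstick.** Simulation with 40,000 trials per setting and n = 10. Spearman's correlation (critical value 0.648) on the continuous change is compared with the exact rank-sum test on response yes/no. A trial with an empty group counts as no rejection.

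| Correlation | Spearman | Rank-sum, 25% response | Gain | Rank-sum, 40% response | Gain |
|---|---|---|---|---|---|
| 0.3 | 11% | 6% | 5.6 | 7% | 4.6 |
| 0.5 | 26–27% | 12% | 14.7 | 15% | 11.6 |
| 0.6 | 39% | 17% | 21.3 | 22% | 16.9 |
| 0.7 | 56% | 25% | 31.4 | 33% | 23.2 |
| 0.8 | 76% | 36% | 39.8 | 47% | 29.0 |

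The exact rank-sum test is coarse at this size, so the comparison was repeated with Pearson's correlation against a t test. The gain is then 12.2 to 40.8 points for correlations 0.5 to 0.8, and 3.5 to 4.4 at 0.3. The gap is therefore not just an effect of the discrete test.

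If the combination were more active, say 50% response, P(0 or 1) falls to 1.1% and the rank-based gain at 0.5 to 0.8 is 11 to 27 points.

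**The case against.** The strongest reply is that the marker work is exploratory and judged by eye, so there is no planned power to lose. That stands. A reader might infer from Step 5 that the plan forfeits 12 to 40 points of power. The documents do not support this: they contain no test, and nothing in them supports a correlation of 0.5 to 0.8.

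Three other strong readings also fail:

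- **That the analysis cannot be run if nobody responds.** Only the between-group display is lost. Per-patient time-series plots, the PD-L1 and T-cell correlation (17.31) and treated versus untreated lesion data (17.4) remain.
- **That every marker-outcome analysis is yes/no.** Sections 17.32 and 17.33 compare pre-treatment measurements with changes at progression. Section 17.4 says response to treatment without defining it as two-level.
- **That most outcome information is discarded.** The cut keeps rather more than half.

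It is also fair that confirmed response and early shrinkage are different quantities. Response needs a second evaluation and takes account of new and non-target lesions; a single-scan target sum does neither. Goal 2.3 names confirmed response. This is a good reason to keep the yes/no display, but not to omit the graded one. Markers come from biopsied skin lesions while target sums span all involved organs, but that weakens both outcomes alike.

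Finally, the gain is limited. At n = 10 a correlation of 0.6 has an approximate 95% interval of −0.05 to 0.89 (Fisher z: 0.693 ± 1.96/√7). Biopsies may be omitted under the note to Section 3.19c, so n may be smaller still. Individual plots for 500 or more genes would be impractical.

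**Conclusion.** The point holds as a low-priority improvement to an exploratory analysis. The responder comparison in Sections 2.3 and 16.5, and in 17.4 as worded, uses a yes/no outcome although a graded one is available from recorded data. The group-size figures (0 or 1 responder in 24.4% or 4.6% of trials) rest only on n = 10 and the single-agent rates in Section 1.9c11. The 54% to 62% information figure also needs bivariate normality. The power gains need, in addition, an assumed correlation and a test that the plan does not contain; at a correlation of 0.3 they nearly vanish. No endpoint, stopping rule or patient is affected. The graded display would remain descriptive: even at a correlation of 0.5, Spearman power is about 27%.

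**What to change.** In Section 16.52, for each immunohistochemistry marker in Section 17.41 (PDL1, PD1, CD3, CD4, CD8):

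- Add scatter plots of the baseline value, the 6-week percent change and the 6-week value against percent change in PBSD from BSD at the first on-treatment evaluation (after cycle 4).
- Give Spearman's correlation with a confidence interval, labelled exploratory.
- Use confirmed response as the plotting symbol, so that goal 2.3 is still shown.
- Mark patients with new lesions or non-target progression, and rank those who progress or die before that scan as the worst outcome.
- State what will be shown if there are 0 or 1 responders.

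For the gene panel in Section 17.42, use a ranked table of gene-wise Spearman correlations with false-discovery-rate control, not individual plots. Leave the response definition in Section 16.21 unchanged for this purpose.

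The cost is a few sentences and some extra analysis, with no new visits, tissue or data. Because a single-scan target sum misses durability and new or non-target disease, the new display supplements the yes/no plots and does not replace them.
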